### **Measurements/Data collection.**

#### Pain assessment:

The adult NVPS will be used to assess pain while patient is intubated in the ICU. This scale is used routinely in intubated and nonverbal critically ill patients in the Cardiovascular ICU (CVICU). The NVPS will be performed by a blinded care provider (e.g. nurse or nurse manager) who is trained on how to use the scale. Time 0 will be designated as the time the patient leaves the OR. The NVPS will be performed every 2 hrs for the first 4 hrs and then every 4 hrs following until the patient is extubated.

The numerical rating scale (NRS) ranging from 0 (no pain) to 10 (worst pain ever) will be used to assess pain

once the patient is extubated and alert. The scale will be administered every 4 hrs for the first 72 hrs post-op.

Cumulate pain scores at time points at 2, 4, 8, 12, 24, 36, 48, 60 and 72 hrs will be compared.

#### Opioid requirements:

All narcotics will be converted to fentanyl equivalents (see Appendix VI) in order to calculate total morphine requirements for each interval. Cumulate morphine equivalents used at time intervals 2, 4, 8, 12, 24, 36, 48, 60 and 72 hours will be calculated.

#### Secondary outcomes:

“ICU length of stay” will be calculated as the time the patient leaves the OR to the time that the patient is deemed appropriate for transfer out of the ICU by the treating physician and nursing staff, in hours.

“Hospital length of stay” will be calculated as the time the patient leaves the OR to the time of discharge, in days.

“Time to extubation” will be calculated as time the patient leaves the OR to the time of extubation, in hours.

“Time to return of bowel function” will be calculated as the time the patient leaves the OR to the time of first recorded bowel movement, in days.

#### Other variables:

Splinting can occur from inadequately controlled pain, resulting in the subject avoiding deep inspiration. The degree of splinting will be measured by a change in bedside inspiratory capacity (IC) at post-operative day 1-2 from preoperative IC.

#### Adverse events will be recorded:

- Adverse cardiac events: angina, myocardial infarction, new cardiac arrhythmia
- Neurologic: transient ischemic attack (TIA), stroke (CVA)
- Gastrointestinal: constipation, ileus, bowel obstruction
- Pulmonary: Pneumonia
- Renal: renal insufficiency
- Wound infection, wound dehiscence

#### Assessment of the blind

Subject responses at follow-up regarding speculation about the treatments received will be compared to each subjects actual group assignment in order to determine adequacy of the blind.

### **Data Analysis.**

#### Data Analysis

- Patient demographics/Pre-op characteristics:
  - Age, sex, race, Body surface area (BSA)/BMI
  - Co-morbid diseases: Diabetes mellitus, COPD, smoking, hypertension, coronary artery disease
  - Left ventricular ejection fraction (%)

- Creatinine (Cr), Cr clearance
- Functional status: New York Heart Association (NYHA) class, American Society of Anesthesiologists (ASA) classification
- Intra-operative characteristics:
  - Operation type: CABG (on/off bypass), AVR, MV repair/replacement, Maze, Other (i.e. TV repair/replacement, ASD closure)
  - Internal mammary artery (IMA) harvested (one or two)
  - Cardiopulmonary bypass time (min)
  - Aortic cross-clamp time (min)
  - Intraoperative fentanyl ( $\mu\text{g}$ ), intraoperative versed (mg)
- Pain assessment:
  - Calculate mean area under the curve (AUC) for adult NVPS scores over the time intervals “0-2”, “0-4”, “0-8” and “0-12” hours.
  - Calculate mean AUC for NRS scores over the time intervals “0-12”, “0-24”, “0-36”, “0-48”, “0-60” and “0-72” hours.
- Opioid requirement:
  - Calculate mean cumulative fentanyl equivalent use for time intervals “0-2”, “0-4”, “0-8”, “0-12”, “0-24”, “0-36”, “0-48”, “0-60” and “0-72” hours.
  - Use of breakthrough pain medication (e.g. Toradol or Tramadol)
- ICU length of stay:
  - Calculate mean lengths of stay (hours) for placebo and Exparel® groups.
- Hospital length of stay:
  - Calculate mean lengths of stay (days) for placebo and Exparel® groups.
- Time to extubation:
  - Calculate mean time to extubation (hours) for placebo and Exparel® groups.
- Time to return of bowel function:
  - Calculate mean time to return of bowel function for placebo and Exparel® groups.
- Splinting
  - Mean change in IC from pre-operative to POD #1-2 in both treatment arms.
- Assessment of blind
  - Calculate the percentage of correctly guessed treatment assignments.

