**Figure 3.** Cross-sectional diagram of DepoFoam® drug delivery system containing aqueous chambers filled with Bupivacaine.

Reproduced from Chahar P, Cummings KC. *Liposomal bupivacaine: a review of a new bupivacaine formulation.* J Pain Research. 2012.

To compare differences in pain control, we will use a number of validated pain assessment tools. These include the adult nonverbal pain scale (NVPS), numerical rating scale (NRS) and brief pain inventory (BPI) (see Appendix II and III). The NVPS has been adopted by the cardiovascular ICU (CVICU) for assessing pain in critically-ill, intubated patients. It includes assessments of the patient’s face, body movements, muscle tension and vital signs to determine a total score ranging from 0 to 10. It has been shown to exhibit high reliability and inter-rater agreement, as well as increase patient and staff satisfaction. The NRS is an 11-point scale ranging from 0, “no pain”, to 10, “the worst possible pain”, that is used by nursing staff for

assessing and documenting pain in extubated, alert patients. The scale has shown high sensitivity and simplicity. Moreover it is interval and allows for parametric analysis. The BPI consists of four questions rating pain severity and seven questions regarding impact of pain on daily function, allowing calculation of pain severity and interference indices for comparison. Studies have shown that BPI scores correlate with the number of days from surgery and decreasing analgesic requirements.

Exparel® is not currently FDA-approved for peripheral nerve blocks. There are two ongoing clinical trials studying the use of Exparel® for femoral nerve blocks. However, Exparel® has not previously been studied for our specific application. Thus, we are conducting this study to evaluate the efficacy and safety of Exparel® in parasternal nerve blocks in cardiac surgery patients. Successful use of Exparel® for parasternal intercostal nerve blocks may revolutionize the management of post-cardiac surgery pain. Optimal pain control and reduced opioid doses would enable earlier extubation and mobilization, less opioid-associated morbidity and shorter ICU and total hospital lengths of stay.

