### Statistical analysis

Descriptive statistics will be reported for each group. Means with standard deviation and 95% confidence intervals of the means will be reported for continuous variables and frequency and proportion distribution will be reported for categorical outcomes.

Student t-test (for normally distributed continuous variables) and Wilcoxon rank sum tests (for non-normally distributed variables) will be used to compare continuous outcomes such as AUC for adult NVPS/ NRS and opioid requirements between the two groups. For categorical outcomes, chi-square tests will be used to compare differences between the two groups. If some cell counts are small and the asymptotic tests are not reliable, then exact methods will be used. A general linear regression model for NRS scores will be applied to show the main effect for the treatment group, adjusting for covariates. Regression analysis will also be applied to opioid requirements. For the binary outcome of whether a patient has reached his/her maximum allowed dose of opioid, logistic regression models will be applied. For the opioid requirement outcome, patients who have reached their maximum allowed dose of opioid will be treated as censored and a Tobit regression model will be applied. Since there are two primary outcomes, a type I error of 2.5% will be used. All the tests will be two-sided.

Survival analyses will be applied for time to event data, such as the lengths of stay and mean time to return of bowel function. Logrank tests will be applied for simple comparisons between the two groups. Cox proportional hazards models will be used to facilitate the inclusion of covariates in the regression analysis. Note that although no censoring of subjects are expected in the study (i.e. the lengths of stay and mean time to return of bowel function will be observed for each patient) and a general linear regression analysis may be applicable, our survival analysis approach enables us to estimate the survival curves and read the different rates at different time points from the curves.

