**Table 2: Study Schedule and Procedures (Cont.)**

Procedure	After Study Drug Administration														
	2-72 Hours														Site Visit
	Time post-drug				0	2	4	8	12	24	36	48	60	72	
	Study Day	Day -30 to -1	Day -1 to 1	1	1	1	1	1	1	2	2	3	3	4	30
	Time Window (±h)					0.25	0.25	0.5	0.5	1	2	2	4	4	96
Oral narcotics												X	X		
Subject's satisfaction with postoperative analgesia									X				X	X	
Brief Pain Inventory	X													X	
Record occurrence and duration of nausea/vomiting					X	X	X	X	X	X	X	X	X	X	
Record date/time of each bowel movement					X	X	X	X	X	X	X	X	X	X	
Record date/time of each rescue pain medication dose					X	X	X	X	X	X	X	X	X	X	
Subject productivity (date subject returned to work or normal daily activities)														X	
Concomitant medications 	X	X	X	X	X	X	X	X	X	X	X	X	X	X	
Record AEs and SAEs					X	X	X	X	X	X	X	X	X	X	

 Clinical labs will include Complete Metabolic Panel, CBC and INR/PTT.

 Temperature, heart rate, blood pressure, oxygen saturation will be monitored continuously in the cardiovascular ICU (CVICU) and at the time points listed.

 Inspiratory capacity (IC) will be measured using the handheld spirometer at baseline (pre-op) and then once between POD #1-2.

 Pain will be assessed with the NVPS or NRS scores at the end of anesthetic and before the first dose of rescue pain medication.

 Pain will be assessed with NVPS if the patient is still intubated and/or sedated. Pain will be assessed with the NRS score if the patient is extubated and alert/responsive.

 All medications that the subject used within 3 days prior to surgery will be recorded; including medication name, dose and date last taken.

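### The NVPS AUC is tested over 0-8 and 0-12 h although NVPS stops at extubation, and no rule covers patients who change scale inside the window

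*Combined protocol and SAP*

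**What the plan says.** Under Measurements/Data collection, Pain assessment, the clock starts when the patient leaves the OR. The schedule is: "The NVPS will be performed every 2 hrs for the first 4 hrs and then every 4 hrs following until the patient is extubated". The NRS then takes over: it is used "once the patient is extubated and alert. The scale will be administered every 4 hrs for the first 72 hrs post-op".

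Appendix I, Table 2 lists both scales at 8 and 12 h. Footnote 5 gives each patient one of them: "Pain will be assessed with NVPS if the patient is still intubated and/or sedated"; patients who are extubated and responsive get the NRS.

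The Data Analysis section nevertheless has the instruction "Calculate mean area under the curve (AUC) for adult NVPS scores over the time intervals", followed by four fixed windows, ending at 2, 4, 8 and 12 h. The Statistical analysis section uses the t-test or Wilcoxon rank sum test to "compare continuous outcomes such as AUC for adult NVPS/ NRS and opioid requirements" between the two groups.

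The Background section states the expectation that "Optimal pain control and reduced opioid doses would enable earlier extubation". Time to extubation is itself listed among the secondary outcomes.

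**The concern.** An area under a score has units of points times hours. If recording stops at extubation, the area depends both on how much pain there was and on how long the patient was intubated. For a patient extubated at 5 h, the 0-8 and 0-12 h windows cannot be filled with NVPS scores.

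The plan does not say what happens then. The AUC could be cut off at extubation, divided by the hours observed, carried forward, joined to the NRS, or restricted to patients still intubated. These choices give different comparisons. The weighted GEE text addresses dropout only in the optional repeated-measures analysis, not in the AUC test.

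At stake is the reading of the early analgesia result. If the AUC is cut at extubation, a difference in hours intubated, whether caused by the drug or by chance, would appear as a difference in pain. It would also count time to extubation a second time.

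**Working it through.** **The plan's own figures.** The documents give no number for NVPS AUC or extubation time. The only related figures are the powers in Number of subjects: 86% (NRS) and 98% (opioid use), at two-sided 2.5%, for a 30% decrease with the SD falling in proportion. For NRS, the difference is 0.3 × 53.2 = 15.96 and the SD is √((24.1² + 16.87²)/2) = 20.80. With 37 per arm after 5% dropout, the normal approximation gives 85.5%; with 39 per arm, the t-test gives 86.2%. Opioid power is 97.4% (37 per arm) or 98.0% (39 per arm). These figures reproduce, and NVPS plays no part in them.

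**Step 1: constant pain, area cut at extubation.** Let both arms have the same constant score *c*. With window *W* and extubation time *T*, AUC = *c* × min(*W*, *T*). The extubation times below are assumptions.

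| Extubation, placebo v drug | Fall in AUC, 0-8 h | Fall in AUC, 0-12 h |
|---|---|---|
| 8 v 7 h | 12.5% | 12.5% |
| 8 v 6 h | 25% | 25% |
| 10 v 8 h | 0% | 20% |
| 6 v 4 h | 33% | 33% |

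For example, with *c* = 3 and 8 v 6 h, AUC is 24 v 18. The 0-2 and 0-4 h areas do not change in these cases, because nobody is extubated before 4 h.

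**Step 2: simulation with varying extubation times.** All inputs except the arm size are assumed: log-normal extubation time with control mean 6 h and SD 2 or 3 h, patient mean NVPS with mean 2 and SD 0.8 in both arms, pain flat over time, 39 per arm, 0-12 h window. The expected fall in AUC is about the shift divided by 6 h: 0.5/6 = 8%, 1/6 = 17%, 2/6 = 33%.

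| Drug arm extubated sooner by | Fall in AUC | Significant at 2.5% | Significant at 5% |
|---|---|---|---|
| 0 h | 0% | no inflation | no inflation |
| 0.5 h | 8% | 5-6% | 9-11% |
| 1 h | 17% | 16-21% | 23-30% |
| 2 h | 33% | 60-77% | 70-85% |

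The 2.5% column uses the only type I error the plan states.

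**Step 3: a different pain model.** With 37 per arm, mean score 3, between-patient SD 1.0, within-patient SD 1.2, log-SD of extubation time 0.4 and 400 runs at 2.5%, false positives over 0-8 / 0-12 h were:
- 2.2% / 2.0% for median extubation 8 v 8 h
- 5.2% / 10.7% for 8 v 7 h
- 23.3% / 38.8% for 8 v 6 h
- 67.0% / 73.3% for 6 v 4 h

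Dividing each area by the hours observed gave 3.0 v 3.0 and 3.0% in both windows at 8 v 6 h.

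**Step 4: limits of the time-weighted mean.** If pain follows *c* + *bt*, its mean up to *T* is *c* + *bT*/2, so it still depends on *T*. With an assumed *b* = 0.2 points per hour and a 2 h shift, the means differ by 0.2 × 2/2 = 0.2 points. At a nominal 5%, the 0-12 h mean then rejects in about 8% of trials (1 h sooner) and 17-19% (2 h sooner). Over 0-4 h it rejects in only 5-7%.

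**Step 5: why 0-4 h needs the same derivation.** In the Step 2 model with means of 6 v 4 h, 59-63% of the drug arm is extubated before 4 h, and the total 0-4 h AUC gives 45-57% false positives at 5%.

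**The case against.** A reader might infer that the plan builds in a bias toward the drug. The documents do not support that. It needs two conditions that they leave open: that the AUC is a plain area cut at extubation, and that the drug arm is extubated sooner. No formula is given; time-averaging, carrying forward or joining the scales removes the shift when pain is flat. Earlier extubation is only hypothesised in the Background, and the anesthetic regimen aimed at it applies to both arms. This objection stands, and the direction is therefore conditional.

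Footnote 5 schedules a score for every patient at 8 and 12 h, so pain is not unobserved; only the NVPS series ends. It also lets NVPS continue in a sedated patient after extubation, slightly wider than the Measurements section. This narrows the point but does not close it, because the AUC is defined on NVPS by name.

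Restricting the analysis to patients still intubated gave no shift when extubation was unrelated to pain. That subset is nevertheless selected after randomisation, and few remain: at 8 v 6 h, 5.8 v 1.6 of 37 at 12 h.

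The magnitudes rest on assumed inputs, and nothing in the documents makes a 2 h shift likely. That is correct; they are illustrations.

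A reader might also infer that the trial's main analgesia result is compromised in the drug's favour. That does not follow either. The power calculation uses NRS and opioid use, and time to extubation is reported separately, so an imbalance could be seen. The NRS AUC also counts from time 0 although NRS starts after extubation. The same handling would work against the drug there: the post-extubation area within 0-12 h was 11.3 v 16.9 at 8 v 6 h in Step 3's model. The opposite directions do not make either comparison sound.

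**Conclusion.** The concern holds in conditional form. The plan tests an NVPS AUC over windows that outlast NVPS observation and gives no rule for the change of scale. On the ordinary reading of AUC, the 0-8 and 0-12 h comparisons partly measure hours intubated. An arm extubated sooner gets a smaller area with no difference in pain; that favours the drug if it shortens intubation, and there is no systematic bias if it does not.

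The size depends on inputs the documents do not give. Within the assumed range it runs from slight (half an hour sooner) to severe (two hours sooner). The priority is moderate: the comparison bears on the primary aim of analgesia but is not the measure the trial is powered on.

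**What to change.** In the Data Analysis section, replace the total NVPS AUC by the time-weighted mean NVPS in every window: the area divided by the hours under NVPS observation within that window. Test it between arms only over 0-2 and 0-4 h. Report 0-8 and 0-12 h descriptively, with the number still on NVPS in each arm and time to extubation alongside.

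The cost is a change of wording and derivation, with no new data. Two NVPS windows become descriptive. The time-weighted mean is only approximately free of the problem when pain changes over time (Step 4), which is why the later windows should not be tested. The documents also do not say how many patients will still be intubated at 4 h, so the number on NVPS should be shown for the tested windows too.

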**Withdrawal Criteria.**

Patients meeting these intra-operative and post-operative criteria will be withdrawn from the study because of the likelihood that these characteristics will independently affect primary and secondary study outcomes. However, primary and secondary outcomes will still be collected for these patients and results included in an “intention-to-treat” analysis.

- Post-operative intubation longer than 16 hours.
- Cardiopulmonary bypass time  $> 3$  hours or aortic cross-clamp time  $> 120$  minutes.
- Return to OR during hospital admission.

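### Every NRS AUC window opens at OR exit but NRS scoring waits for extubation; with no rule for the gap, a total observed area would count against any arm extubated sooner

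*Combined protocol and SAP*

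**What the plan says.** The Pain assessment item under Data Analysis reads "Calculate mean AUC for NRS scores over the time intervals “0-12”, “0-24”, “0-36”, “0-48”, “0-60” and “0-72” hours". A separate line gives NVPS its own AUC over 0-2, 0-4, 0-8 and 0-12 h.

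Under Measurements/Data collection, the clock is set by "Time 0 will be designated as the time the patient leaves the OR". The NRS is used "once the patient is extubated and alert. The scale will be administered every 4 hrs for the first 72 hrs post-op". Footnote 5 to Table 2 in Appendix I agrees: "Pain will be assessed with the NRS score if the patient is extubated and alert/responsive". Until extubation the NVPS is used. The same Measurements section adds: "Cumulate pain scores at time points at 2, 4, 8, 12, 24, 36, 48, 60 and 72 hrs will be compared".

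Time to extubation is a secondary outcome that "will be calculated as time the patient leaves the OR to the time of extubation, in hours". The Background expects good pain control to bring earlier extubation. One withdrawal criterion is "Post-operative intubation longer than 16 hours", but "primary and secondary outcomes will still be collected for these patients" and they enter an intention-to-treat analysis.

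The Statistical analysis section compares the NVPS and NRS AUCs between groups by t-test or Wilcoxon test. It also plans a covariate-adjusted linear regression for NRS scores, and mixed and GEE/WGEE models for the repeated scores.

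**The concern.** An area grows with pain level and with the time over which it accrues. Here the accrual time starts at extubation, which happens after randomisation, is compared between arms, and is expected to come earlier if the block works. If only observed NRS is integrated, a patient extubated sooner collects more area at the same pain level. A real pain benefit that also shortens intubation would then be understated.

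The text does not bridge the gap. It does not join NVPS to NRS, impute the early hours, use the pre-operative NRS as an hour-0 value, divide by observed time, or set a common start. Nor does it say what value a patient extubated after the window closes receives. Pain is one of the two primary outcomes, so the pain comparison could turn on a computing choice made after the data are seen.

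**Working it through.** **Inputs.** Window ends W = 12, 24, 36, 48, 60, 72 h and the start at hour 0 come from Data Analysis; NRS from extubation onward comes from Measurements/Data collection and Table 2. Extubation time t is not given anywhere, so every t below is an assumption. The plan states no figure for the AUC that could be reproduced. Its 86% power refers to a 30% decrease in mean NRS scores and is not re-examined here.

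**Step 1: which reading is plainest.** In the Data Analysis list, the mean of length of stay, time to extubation and cumulative opioid use is in each case a mean over patients. Mean AUC fits that pattern better than a time average. Separate NVPS and NRS lines that both cover 0-12 h weigh against a joined curve.

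**Step 2: raw observed area, constant pain.** With pain level P, area = P × (W − t). For equal pain, the excess in the sooner arm is (W − t_sooner)/(W − t_later) − 1. A true 30% reduction in that arm would read as 1 − 0.7 × (1 + excess). With 5 h versus 7 h:

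| Window | Ratio | Excess area | True 30% reads as |
|---|---|---|---|
| 0-12 h | 7/5 | 40.0% | 2.0% |
| 0-24 h | 19/17 | 11.8% | 21.8% |
| 0-36 h | 31/29 | 6.9% | 25.2% |
| 0-48 h | 43/41 | 4.9% | 26.6% |
| 0-60 h | 55/53 | 3.8% | 27.4% |
| 0-72 h | 67/65 | 3.1% | 27.8% |

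With equal extubation times the ratio is 1 and the excess is 0.

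**Step 3: difference that would cancel a 30% reduction.** This is (W − t_later) × (1/0.7 − 1). With the later arm at 6 to 10 h, it is 2.57 to 0.86 h for 0-12 h and 7.71 to 6.00 h for 0-24 h. Full cancellation is realistic only in the first window.

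**Step 4: the time grid matters.** If NRS is taken at fixed 4-hourly points from hour 0, patients extubated at 5 h and 7 h both start at 8 h and differ by 0%. Patients extubated at 7 h and 9 h start at 8 h and 12 h. They differ by 16/12 − 1 = 33.3% over 0-24 h and 64/60 − 1 = 6.7% over 0-72 h, and the later patient has no area in 0-12 h.

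Averaging over assumed lognormal extubation times (medians 6, 8, 10 h; log-SD 0.4; limits 2-16 h) shifted 2 h earlier, with scoring from extubation, from the next 4-hourly point, or from that point but not before 8 h, gives an excess of 17.6-100.6% (0-12 h), 4.3-14.7% (0-24 h) and 1.0-3.2% (0-72 h). Using only the Table 2 times (8, 12, 24 h and later) gives up to about 25% at 0-24 h and 4-4.5% at 0-72 h. These ranges are scenarios, not bounds.

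**Step 5: time-weighted mean instead.** For constant pain, P(W − t)/(W − t) = P, so the bias is 0. For pain halving every H hours, with k = ln 2/H, the mean is [exp(−kt) − exp(−kW)]/[k(W − t)]. With the later arm at 6-10 h and the other arm 2 h sooner, the sooner arm's mean is 1.0-2.4% too high for H = 36-72 h in any window. A true 30% reduction then reads as 28.4-29.3%. Under the same decline, the raw area for 5 h versus 7 h is 41-43% (0-12 h), 13-14% (0-24 h) and 4.2-5.5% (0-72 h) too high.

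**Step 6: sparse windows.** On the 4-hourly grid, a patient extubated between 8 and 12 h has one NRS in 0-12 h. Area over hours is then 0/0. Under the Step 4 distributions this is roughly 20-44% of patients, and a further 4-33% have none.

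**The case against.** The strongest reply is that the bias needs two things the documents do not state: that AUC means total observed area, and that extubation times differ by arm. Appendix IV lists no pain score among the extubation criteria, so the difference may be small. Comparing cumulated pain scores from 2 h, when many patients would still be on NVPS, suggests a joined curve; both scales run 0-10 with the same action threshold of 4. This stands as far as it goes. The direction and size are conditional, and only the missing rule is certain.

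It is also fair that other planned analyses do not accumulate hours: the covariate-adjusted regression for NRS scores and the mixed and GEE/WGEE models. The longitudinal models are introduced as a possible refinement and then worded as a commitment. Neither they nor the regression are ranked above the AUC test, so they limit the damage without removing the ambiguity.

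A reader might go further and infer that the trial's pain result is biased, that a true benefit would be reversed, or that the sample size is wrong. The documents support none of these. No extubation hours are given, reversal is plausible only at 0-12 h, and the effect is small by 72 h. The powered quantity is a mean NRS score, with a planning value of 53.2 that cannot be a single 0-10 score, so no power loss can be derived. That no NRS window is named as primary is a separate matter.

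**Conclusion.** The concern holds in conditional form and should be fixed before unblinding. It is certain that the NRS AUC is undefined for the hours before extubation and for patients without NRS in a window. On the plainest reading, total observed area, the comparison confounds pain intensity with time to extubation and works against the arm extubated sooner. The 5 h versus 7 h illustration falls from 40% in the first window to 3.1% in the last, so the matter is mainly one for the early windows. These sizes rest on assumed extubation times, constant pain and scoring from the moment of extubation. The direction needs a difference in extubation between arms, and a time-averaged or joined AUC would largely remove the bias. The NVPS AUC has the mirror problem: it stops accruing at extubation, so its raw area favours the arm extubated sooner.

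**What to change.** In Data Analysis and Statistical analysis, replace the raw NRS AUC with a time-weighted mean NRS per patient: area over the observed part of the window divided by the hours observed. Where a patient has one NRS in the window, use that score. State before unblinding how a patient with no NRS in the window enters the intention-to-treat analysis. Report the planned longitudinal model beside this comparison, and present the NVPS AUC descriptively together with time to extubation.

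The cost is wording only: the scores are already scheduled, and no assessment or clinical procedure changes. There are two drawbacks. Averaging still begins at a post-randomisation time, so the small residual bias in Step 5 remains if pain declines. A mean resting on one score is also less precise than one resting on many, which matters most in 0-12 h.

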## II. CHARACTERISTICS OF THE RESEARCH POPULATION

### Number of subjects.

The study will include 78 patients, 39 patients in the study drug arm and 39 patients in the control arm. Since there are two primary outcomes, we set the type I error at 0.025 for the power analysis. Based on results from a prior study by Barr et al., we assumed a baseline Numerical Rating Scale (NRS) score for pain of 53.2 with standard deviation of 24.1 and a baseline cumulative morphine requirement over 24 hours of 23.2 mg with standard deviation of 8.3 mg. The proposed sample size was calculated to achieve 86% power to detect a 30% decrease in mean NRS scores at the 2.5% level of type I error (two-sided). This sample size also provides for a 98% power to detect a 30% decrease in total opioid consumption over the first 24 hours post-operatively. Note that we assumed the standard deviation decreases accordingly. A 5% drop out rate was included into the sample size calculation.

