### Patient enrollment

Screening procedures will be performed in the outpatient clinic, inpatient floor or cardiac cath lab. During the screening visit, medical/surgical history, vital sign measurements, and routine clinical laboratory tests, which are normally obtained in all cardiac surgery patients (complete metabolic panel, CBC, INR/PTT). If the patient meets eligibility criteria and is willing to participate, then informed consent will be obtained. Consenting patients will also undergo drug/alcohol screening and forced vital capacity (FVC) measurement prior to surgery. The patients will be trained on the pain assessment tools used during the study, including the adult NVPS and NRS (see Appendix II).

Prior to the planned operation, patients will be administered the Brief Pain Inventory to establish baseline pain scores (see Appendix III). The patient will also receive a sheet reviewing the NVPS and NRS pain assessment scales and be asked to rate their pain on the NRS scale. They will also be instructed on how to use the PCA pump prior to surgery.

On the day of surgery, the subjects' history, physical and labs will be reviewed by research staff to confirm study eligibility. They will also be instructed on how to use the incentive spirometer and their peak inspiratory capacity (IC) will be measured.

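### Splinting is planned as a comparison of raw change in inspiratory capacity; adjusting for the pre-operative value already being collected would be a nearly free gain in precision

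*Combined protocol and SAP*

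**What the plan says.** The Other variables section defines the measure: "The degree of splinting will be measured by a change in bedside inspiratory capacity (IC) at post-operative day 1-2 from preoperative IC". The Data Analysis list repeats it as a mean per arm: "Mean change in IC from pre-operative to POD #1-2 in both treatment arms".

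Baseline is planned for all subjects. Under Patient enrollment, on the day of surgery, "their peak inspiratory capacity (IC) will be measured". The footnote to Table 2 fixes the number of readings: "Inspiratory capacity (IC) will be measured using the handheld spirometer at baseline (pre-op) and then once between POD #1-2". So each patient should have one value before surgery and one after.

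The Statistical analysis section says that the t-test or Wilcoxon test "will be used to compare continuous outcomes such as AUC for adult NVPS/ NRS and opioid requirements between the two groups". IC is not named there but falls under continuous outcomes. Regression is assigned elsewhere: "A general linear regression model for NRS scores will be applied to show the main effect for the treatment group, adjusting for covariates", and "Regression analysis will also be applied to opioid requirements". Cox models with covariates are planned for time-to-event outcomes. Neither that section nor any other names pre-operative IC as a covariate.

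The section on number of subjects gives 39 patients per arm and powers only the pain score and the opioid requirement. No mean, SD, correlation or power is given for IC.

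**The concern.** A change score fixes the coefficient of the baseline value at 1. The coefficient that minimises the variance is rk, which equals 1 only by coincidence. When it differs from 1, the change score carries baseline variation that a regression would take out.

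There is a second cost. Randomisation is in blocks of 4 with no stratification described, so baseline IC is balanced between arms only by chance. In a trial of 78 patients an ordinary imbalance is not negligible, and an unadjusted change comparison passes part of it into the estimated treatment difference.

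What is at stake is the chance of seeing an effect on pain-limited breathing. Forced vital capacity is measured before surgery, but the schedule shows no post-operative reading. IC is therefore the only lung-function measure planned both before and after the operation.

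**Working it through.** **The plan's own figures.** There is no IC figure to reproduce. The power statement for the primary outcomes was checked to settle the sample size.

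- 39 per arm with 5% dropout leaves 39 × 0.95 ≈ 37 evaluable.
- The SD in the treated arm is taken as 30% lower, as the plan assumes. For the pain score, the pooled SD is sqrt((24.1² + 16.87²)/2) = 20.8 and the difference is 0.3 × 53.2 = 15.96.
- At two-sided 2.5%, normal-approximation power is 85.5% with 37 per arm and 87.4% with 39, against 86% stated.
- For opioid use it is 97.4% and 98.0%, against 98% stated.

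The stated figures reproduce, and none of them involves IC.

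**Variance comparison.** Let r be the correlation of pre- and post-operative IC, and k the post-operative SD divided by the pre-operative SD. Both are assumptions. In units of the pre-operative variance:

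- change score: 1 + k² − 2rk
- adjusted for baseline: k²(1 − r²)
- difference: (1 − rk)²
- share removed by adjustment: (1 − rk)² / (1 + k² − 2rk), which is (1 − r)/2 when k = 1

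The share is never negative. For r below 1 it is zero only when rk = 1, which needs a post-operative SD above the pre-operative one.

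Worked cases:

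- r = 0.5, k = 1: 0.25/1.00 = 25%
- r = 0.5, k = 0.5: 0.5625/0.75 = 75%
- r = 0.8, k = 1.2: 0.0016/0.52 = 0.3%

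Share of variance removed:

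| r | k = 0.5 | k = 0.7 | k = 0.8 | k = 1.0 | k = 1.2 |
|---|---|---|---|---|---|
| 0.5 | 75% | 53.5% | 42.9% | 25% | 12.9% |
| 0.7 | 76.8% | 51.0% | 37.2% | 15% | 3.4% |
| 0.8 | 80% | 52.3% | 36.0% | 10% | 0.3% |
| 0.9 | 86.4% | 59.5% | 39.2% | 5% | 2.3% |

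**In patients.** With equal SDs, 39 per arm with adjustment matches 39/0.75 = 52 per arm on change scores at r = 0.5, but only 39/0.95 ≈ 41 at r = 0.9.

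**In power.** Suppose a change-score comparison had 80% power at two-sided 5%. Adjustment that removes a share g raises this to Φ(2.80/sqrt(1 − g) − 1.96): 82% for g = 5%, 86% for g = 15% and 90% for g = 25%.

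**Small-sample cost.** With 74 evaluable patients and one normal covariate, estimating the slope inflates the variance by a factor of about 1 + 1/(74 − 4) = 1.014. Simulation with 37 per arm agrees broadly with theory:

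- r = 0.7, k = 1: 14.7% removed (theory 15%)
- r = 0.5, k = 1: 23.0% (theory 25%)
- r = 0.5, k = 0.5: 74.3% (theory 75%)
- r = 0.9, k = 1: 2.7% (theory 5%)

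In the 0.3% corner, adjustment would lose about 1%: 0.997 × 1.014 = 1.011.

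**Chance imbalance.** A one-standard-error difference in baseline IC is sqrt(2/39) = 0.23 baseline SD. With an assumed slope rk = 0.5, it moves the change-score difference by 0.5 × 0.23 ≈ 0.11 SD against the arm with the higher baseline. Adjustment removes that shift.

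**The case against.** The strongest reply is that nothing here is an error. In a randomised trial, change scores estimate the same treatment difference as the adjusted model, without bias and with the type I error intact. That stands: this is a matter of precision.

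A second reply is that the Data Analysis list mostly says what to calculate and does not fix the test. It asks for mean lengths of stay, for instance, which are then analysed by log-rank and Cox methods. That also stands in part. The unadjusted test for IC follows from the general wording for continuous outcomes, so the plan under-specifies IC rather than choosing a poor test expressly. If the Wilcoxon branch were used, the variance ratios above would not carry over directly.

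A third is weight. IC is outside the listed secondary outcomes and is not powered. That stands and sets the severity.

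Three stronger readings are tempting, and the documents support none of them:

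- A reader might infer a definite gain, such as 15% to 75% of the variance. Those ends are only the pairs r = 0.7, k = 1 and r = 0.5, k = 0.5. Neither is a bound, and the documents give neither r nor k.
- A reader might infer that raw change mainly reflects body size, because larger lungs lose more volume. The documents say nothing about how IC loss scales. Baseline explains the same share of the change score that adjustment removes, which at k = 1 is 25% or less for the correlations tabulated.
- A reader might extend the point to the 30-day Brief Pain Inventory. The analysis sections name no analysis for it, so there is no change-score comparison to replace.

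**Conclusion.** The point holds as a low-severity, nearly free improvement. The plan summarises raw change in IC, plans a baseline value for everyone, and specifies no model that uses the baseline as a covariate. The comparison is valid but less precise than it could be, and it is exposed to chance imbalance.

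The gain is conditional on r and k. It is 5% to 25% of the variance for r from 0.9 down to 0.5 with equal SDs, much larger if the spread of IC shrinks after surgery, and close to nothing if it widens. The cost is about 1% to 2% of variance. The calculation assumes a linear relation, complete pairs of IC readings and roughly 37 evaluable patients per arm; baseline readings are planned, not assured. The sample size and the primary conclusions do not depend on it.

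**What to change.** Add one sentence to the Statistical analysis section: IC will be analysed by a linear model with treatment arm and pre-operative IC as terms, reporting the adjusted difference between arms with its 95% confidence interval.

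The definition under Other variables and the mean change in the Data Analysis list can stay as the descriptive summary. Using change as the outcome with pre-operative IC as a covariate gives the same treatment estimate as using post-operative IC; only the baseline slope differs, by exactly 1.

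The cost is wording in the plan and one estimated slope. No new data, visits or patients are needed. The sentence should be fixed before unblinding.
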